Studies of the upper and lower airways of human infants with RSV bronchiolitis are required to definitively understand pathological mechanisms. Studies in infants are difficult to undertake, especially as the child may be clinically unstable and conventional procedures to obtain samples may be too invasive. Infants who require mechanical ventilation for severe RSV bronchiolitis are tracheally intubated, sedated and have indwelling vascular catheters. This allows access to the respiratory tract and enables blood sampling.

In infants naturally infected with RSV, the presence of virus is generally detected in nasopharyngeal aspirate (NPA) samples (5;9). In the UK it is standard clinical practice to perform NPA sampling by direct suction of secretions. However, because this involves the introduction of a suction catheter into the nostril and then to the back of the nose, this procedure may be relatively unpleasant. Sampling by NPA has been found superior to nasal swabs manufactured from natural products (10;11).

Using nasal swabs in young children is rapid and painless and also accurate for RSV diagnosis (12). There is concordance between nasal and nasopharyngeal (NP) swabs for viral testing (13). In a comparison with NPA, nose and throat swabs were more comfortable and have less risk of harm in a clinical setting, but NPA is still recommended in a hospital context (14). Flocked nylon swabs gave higher viral loads than cotton swabs when using qPCRs for detection of human rhinovirus (15).

Viral load may be obtained from these samples by quantitative polymerase chain reaction (qPCR) of infectious samples. This correlates with disease severity in infected infants (4;5). In adults infected experimentally with RSV, the viral load peaks before maximal clinical symptoms (6). It is a major parameter in quantitating the magnitude of infection (7). In assessing the effects of novel therapeutics in experimental infection, the area under the curve (AUC) of viral load is generally the primary end point (8). To determine this, daily samples over the disease course are required. However, there are concerns regarding the accuracy of viral load detection from routine NPA samples as this is dependent of the amount of mucous suctioned at the same time, which varies enormously from patient to patient.

The current methods of sampling described above have a number of limitations:

- Samples are often diluted in saline which can lead to poor sensitivity

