- There is a lack of consistency in the location the sample is obtained from which can affect both diagnostic specificity and reproducibility
- Sampling can be uncomfortable and invasive

Proposal for novel absorption sampling methods

In conjunction with a specialist medical device manufacturing company (Hunt Developments (Midhurst, West Sussex) we have produced novel nasosorption and bronchosorption kits that have CE marking. Both nasosorption and bronchosorption methods use synthetic absorptive matrix (SAM) strips: that look and feel like blotting paper, and will be placed onto the mucosal surface. These are comfortable to use and can be used at frequent intervals over extended periods of time. This non-invasive technique is ideal for infants and children, and it is possible to obtain neat mucosal lining fluid (MLF) even from normal healthy noses. The eluates contain cytokines and chemokines at high detectable levels on multiplex immunoassay.

We would like to use these SAMs to take MLF samples from the nasal and bronchial mucosal surfaces to see if these novel techniques can overcome the problems with current sampling methods. We plan to use these absorption techniques to measure RSV viral load. We also aim to look at the immune response in terms of the anti-viral interferon response (IFN- γ , IFN- λ , IFN- α 2a, IP10, ITAC). In therapeutic studies in the future, it may be possible to document levels of drug (pharmacokinetics) in nasal MLF.

Nasosorption (NS) and bronchosorption (BS)

NS involves using a synthetic absorptive matrix (SAM) to absorb mucosal lining fluid (MLF) in a precise manner from the inferior turbinate. At Imperial College we have used NS in children with allergic rhinitis (16), infants with a family history of atopy (17), and in atopic adults after nasal allergen challenge (NAC) (18). SAM has also been used after experimental human rhinovirus challenge in asthma when both NS and BS were performed (19;20). The [name] group at Imperial have recently compared and validated a variety of SAMs (21), and performed a nasosorption study after cat NAC (22).

The swabs are medical devices, have small handles and are enclosed in a sampling tube. These devices are CE-marked, clean and sterile, and produced in a specialist medical device factory.

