In summary this study will compare the novel methods of NS and BS with the standard technique of nasopharyngeal aspiration (NPA) and routine ETT suction. We shall assess the samples for diagnosis of RSV, viral load and immune responses in the airways of babies with RSV infection. We shall also assess the genetics of babies included in this study, to see if they may be vulnerable to RSV infection.

AIMS

The study involves obtaining nasal samples from babies with suspected RSV infection in the emergency department (ED), as well as those admitted to the paediatric wards and PICU at St. Mary's Hospital, London. This will help us to understand the epidemiology of and the host response to RSV infection in infants both hospitalised and in the community. In addition, we shall take nasal samples from infants attending hospital for outpatient appointments, routine elective surgery and admitted to PICU for non-respiratory diagnoses as controls.

The specific aims are:

1. To study different sampling methods; comparing the established method of NPA and tracheal suction to nasosorption and bronchosorption. We will assess sample volumes, clinical tolerability and virology results: especially viral load.
2. To assess the safety and validity of using bronchosorption to take bronchial MLF samples.
3. To study severity of disease and correlate this with quantitative RSV PCR.
4. To study the incidence of RSV A and B infection, different subtypes of RSV infection.
5. To measure the nasal and bronchial mucosal immune response: in terms of cytokines and chemokines, especially those relating to interferons.

6. To identify if there is a genetic predisposition to severe RSV infection
7. To understand feasibility of these sampling processes in preparation for an interventional study potentially in winter 2017-8.

ENDPOINTS

To compare SAM and nasopharyngeal aspirate (NPA) as sampling methods for measuring RSV viral load.

PRIMARY ENDPOINT: RSV viral load

Virology: How do SAM and NPA compare for RSV viral load determination?

We shall also assess:

- Sensitivity, specificity, quantitation
- Utility for RSV-A vs RSV-B

SECONDARY ENDPOINTS

1. Immune Response: Establishing the use of nasal and bronchial sampling to measure the host immune response to RSV. These techniques could then be applied to the study of drug pharmacokinetics for new therapeutics in future clinical studies.

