Bronchosorption: Following clearance of excess mucus by suction, we will introduce the SAM device that will be passed down the ETT to collect bronchial MLF. The device will be passed into the ETT in the same way that a routine suction catheter is introduced. The device will be introduced by the consultant paediatric intensivist or lead physiotherapist gently to a maximum distance of 10cm beyond the end of the ETT, or until it impacts in the bronchial tree. It will then be withdrawn by 5cm and the SAM paper will then be extruded. The device will then be kept in this position for 10 seconds to allow for maximal absorption. The SAM will then be retracted into the device and the device will be withdrawn.

NB for the 2016-2017 season we will not be carrying out the bronchosorption procedure as we have concerns regarding the device and this is being revised accordingly.

Bronchial aspirate:

Routine clearance of excess mucus by suction through the endotracheal tube. We will keep this aspirate that is usually discarded.

Nasopharyngeal aspirate:

NPA will be carried out after the Nasal SAM has been performed. NPAs will be collected using a standardized protocol (23-25). The child is supine and a small suction catheter is used to take fluid from the back of the nose directly with no saline flush is a routine method used to suction babies with a blocked nose in clinical practice.

In babies who are admitted to the ward, sampling will have to consider the impact of nasogastric and other tubes in the airway. If both NS and NPA ~~all~~ samples have to be taken from the same nostril there should be a 10 min interval between each sample

Blood sampling:

If the baby is having a blood test as part of their routine hospital care an additional 1mL will be taken and used to measure markers of infection and inflammation, together with genetic analysis (subject to consent). If the baby requires further blood tests for clinical reasons, we may take further 1ml research samples at up to 2 further time points to see changes in the immune response.

A 1ml blood sample will be taken at the first time point for genetic analysis as detailed below.

Blood Genetics Methods

- i. **Sample collection** Blood samples from the baby will be collected and genetic material extracted

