- ii. **Sample processing** To carry out genetic analysis from DNA/RNA isolated from infants by targeted gene sequencing, next generation sequencing or whole genome SNP typing in order to evaluate any genetic deficiencies.
- iii. **Data Collection** It will be necessary to collect demographic and clinical data from the families in order to define clearly clinical phenotypes. This will include data on age, sex, ethnic groups and clinical details relating to the phenotype. These clinical data will be provided by collaborating clinicians from participating hospitals.

INCLUSION AND EXCLUSION CRITERIA

Group 1 and Group 2

Inclusion Criteria

- Infants aged 2 weeks-24 months
- Presentation to the Emergency Department with any upper respiratory tract infection (URTI) in the RSV season (Oct-March).
OR
- Documented RSV infection, admitted to the paediatric wards at St Mary's Hospital.

Exclusion Criteria

- Any local or systemic factor that would influence the safety of nasal sampling.
- Bilateral indwelling nasal catheters or local nasal pathology preventing access for nasal sampling.
- Bleeding disorders.
- The baby is taking part in another interventional study.
- The parents or guardians not able to sign the informed consent from due to limited English or comprehension despite the use of independent interpreter services.
- Limited life expectancy of the baby,

Group 3

Inclusion criteria

- Hospitalised Infants admitted to the PICU at St. Mary's Hospital, aged 2 weeks-24 months with documented RSV infection (by rapid test and/or PCR).
- Infants of weight >2kg.
- On a conventional ventilator with an Endotracheal Tube (ETT) of ≥ 2.0 mm diameter

Exclusion criteria

- Any local or systemic factor that would influence the safety of nasal sampling.
- Bilateral nasal catheters or local nasal pathology preventing access for nasal sampling.
- The baby is taking part in another interventional study.
- Prematurity - corrected gestational age <36 weeks, weight <2kg
- Significant hypoxia or instability precluding ventilator disconnection
- Transcutaneous oxygen saturation of <95% on 60% oxygen
- Risk of bleeding
- Pneumothorax
- Infants receiving oral corticosteroid therapy at any time in past month
- Parents or guardians not able to sign informed consent from due to limited English or understanding despite the use of independent interpreter services.
- Limited life expectancy or a decision to limit management.

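### Sensitivity and specificity are planned for SAM versus NPA with no reference standard; scored against NPA, as Group 1 allows, SAM can at best tie

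*Combined protocol and SAP*

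**What the plan says.** The Endpoints section makes RSV viral load the primary endpoint and asks how SAM and NPA compare. The first additional assessment beneath it reads "Sensitivity, specificity, quantitation". No reference standard, positivity cut-off, analysis group or unit of analysis is given. Data Analysis deals only with inflammatory mediators and biomarkers.

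The endpoint names NPA alone. The Summary says the study will "compare the novel methods of NS and BS with the standard technique of nasopharyngeal aspiration (NPA"), and adds routine suction of the endotracheal tube. The Proposal section gives the reason for using SAM: "to see if these novel techniques can overcome the problems with current sampling methods". The limitations listed just before it include "Samples are often diluted in saline which can lead to poor sensitivity", and inconsistent sampling location, "which can affect both diagnostic specificity and reproducibility". The background adds that "there are concerns regarding the accuracy of viral load detection from routine NPA samples". Under Procedures, study NPA is taken "directly with no saline flush".

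Study Design and the entry criteria give this picture (30 infants per group; NS is nasosorption, the nasal SAM sample):

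| Group | RSV status at entry | NS | NPA |
|---|---|---|---|
| 1 (emergency department) | open | each nostril | yes |
| 2 (wards) | positive | repeated | daily |
| 3 (ventilated) | positive, by rapid test, PCR or both | repeated | daily |
| Control 1 | no test named; no respiratory symptoms | once | none |
| Control 2 (ventilated) | PCR negative | repeated | daily |

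The Group 2 criterion is "Documented RSV infection, admitted to the paediatric wards". Group 3 and Control Group 2 also give bronchial aspirates.

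**The concern.** Sensitivity and specificity need a reference that says who is infected. The plan names none, so an analyst has to choose one, and NPA is the natural default because it is the named comparator and the usual technique. In Group 1 the sampling schedule offers nothing else.

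Scoring SAM against NPA assumes that NPA is always right. The study was set up partly because current sampling may not be right. Under that scoring no result can show SAM to be the better detector, and each extra true infection that SAM finds lowers its apparent specificity. The study is meant to prepare for an interventional study (Aims, item 7), so a detection summary that can only favour NPA could mislead the choice of sampling method.

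**Working it through.** The documents give no accuracy or prevalence figure, so there is no stated figure to reproduce. The inputs below are assumptions; only n = 30 comes from the plan.

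**Notation.** p = RSV prevalence in Group 1; a, b = true sensitivity of NPA and SAM; both true specificities 100%; d = probability that an infected infant is SAM-positive and NPA-negative. For b ≥ a, d runs from b − a (misses shared as far as possible) to b(1 − a) (independent misses).

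**SAM scored against NPA.**
- Apparent sensitivity = (b − d)/a
- Apparent specificity = 1 − p·d/(1 − p·a)

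**Base case: p = 0.40, a = 0.85, b = 0.95**, so 1 − p·a = 0.66.
- Shared misses, d = 0.10: sensitivity 0.85/0.85 = 100%; specificity 1 − 0.040/0.66 = 93.9%.
- Independent misses, d = 0.95 × 0.15 = 0.1425: sensitivity 0.8075/0.85 = 95%; specificity 1 − 0.057/0.66 = 91.4%.

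A true gain of 10 points in sensitivity therefore reads as a loss of 0–5 points in sensitivity and 6–9 points in specificity, against NPA's automatic 100%/100%.

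**Ranges.**

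| True NPA / SAM sensitivity | Prevalence | Apparent SAM sensitivity | Apparent SAM specificity |
|---|---|---|---|
| 85% / 95% | 30–60% | 95–100% | 82.6–96.0% |
| 75% / 85% | 30–60% | 85–100% | 76.8–96.1% |
| 90% / 100% | 30–60% | 100% | 87.0–95.9% |
| 85% / 75% (SAM worse) | 40% | 75–88.2% | 93.2–100% |

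In the last row a true deficit of 10 points reads as 12–25 points.

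**Direction.** Because d ≥ b − a, (b − d)/a never exceeds 1. If b > a then d > 0, so apparent specificity is below 100%. With no true false positives, this holds whatever values are assumed.

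**Worked counts.** Suppose 12 of 30 are infected, NPA finds 10, SAM finds 11, and neither has a false positive. The overlap is 9 or 10.

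| Both + | SAM only | NPA only | Both − | SAM given NPA | NPA given SAM | SAM − NPA positive |
|---|---|---|---|---|---|---|
| 9 | 2 | 1 | 18 | 9/10 and 18/20 | 9/11 and 18/19 | 1/30 = 3.3 points |
| 10 | 1 | 0 | 19 | 10/10 and 19/20 | 10/11 and 19/19 | 1/30 = 3.3 points |

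The paired difference and the second direction of agreement show SAM ahead, which the first direction alone cannot do.

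**Precision.** Clopper-Pearson 95% intervals: 9/10 gives 55.5–99.7%; 18/20 gives 68.3–98.8%. For the first row, the Wald standard error of the paired difference is √(3 − 1/30)/30 = 0.057, so the interval is about −8 to 15 points. In the base case the expected difference is p(b − a) = 4 points, or 1.2 of 30 infants (0.9 to 1.8 over prevalence 30–60%). An exact McNemar test needs at least 6 discordant pairs, all one way, for two-sided p < 0.05 (p = 0.031).

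**The case against.** **The plan never calls NPA the reference.** The endpoint question is symmetric, and standard technique may mean only usual practice. Entry status supplies another comparator: Groups 2 and 3 (60 infants) are documented positive, Control Group 2 (30 infants) is PCR negative, and all three give both NS and NPA. Against entry status SAM could come out ahead. This stands. A reader might infer that NPA is the reference, or the only one available; the documents support neither. The defect is an undesignated reference. What remains is that entry status is not designated either, its specimen is unstated, the background says RSV is generally detected in NPA, and it does not cover Group 1. Bronchial aspirate has the same gap.

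**The documents hardly show that NPA misses infections.** Dilution may not apply, since study NPA uses no flush. The concern about mucus amount is about quantity. Location is tied to specificity and reproducibility. This also stands. The point is only that, if NPA does miss infections, these measures could not show it.

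**A reader might also count misclassified infants in Groups 2 and 3** by applying an assumed NPA miss rate to all 60. That treats study NPA as independent of the entry test. If entry itself rested on NPA and misses are shared, the expected number falls towards zero, so no count is offered.

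**Renaming the measures as agreement changes nothing by itself.** Agreement of SAM given NPA is numerically the same as sensitivity and specificity against NPA. Correct, which is why both directions and the paired difference are needed.

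**Conclusion.** The concern holds in limited form. The plan lists sensitivity and specificity without a reference standard. In Group 1 they can be scored only against NPA, and that scoring cannot show SAM better and counts SAM-only infections as errors. That consequence follows by definition. Its size rests on assumed prevalence and sensitivities, on 100% true specificity for both methods, and on misses between independent and maximally shared; in the base case SAM reads 95–100% sensitive and 91–94% specific. If SAM has true false positives, some SAM-only results are real errors, and scoring against NPA cannot separate the two.

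A reader might infer that the trial's conclusion on detection would be reversed. The documents do not support that. The expected Group 1 difference is 1 to 2 infants, the intervals are wide, and the paired results are collected in any case. These are additional measures in a pilot, and the primary paired viral load comparison is unaffected. The wording should still be corrected before analysis.

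**What to change.** - State that NPA is a comparator, not a reference standard, and define the cut-off for an RSV-positive result by each method.
- **Group 1:** replace sensitivity and specificity with the paired SAM-NPA 2x2 table, positive and negative agreement in both directions, and the paired difference in proportion RSV-positive (SAM minus NPA) with a CI. Use one pre-specified NS-NPA pair per infant and state the rule for the two nostril samples; counting either nostril as positive gives SAM two chances against one.
- **Groups 2 and 3 and Control Group 2:** report the proportion positive by SAM and by NPA side by side against entry RSV status, separately by group and with one pre-specified pair per infant. Note that the entry specimen may be NPA.
- **Control Group 1:** leave out of SAM-NPA agreement, because it has no NPA.

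The cost is endpoint and analysis wording, with no new samples. The downside is that there will be no single accuracy figure for SAM, and the results will be descriptive. Even 30/30 negative in Control Group 2 gives an interval of 88.4–100%.

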Bronchosorption (BS) involves a similar method to NS with a similar SAM material. The SAM is attached to a plastic reinforced catheter that can be introduced through an endotracheal tube to access the bronchial mucosa. [name] [name], respiratory consultant at St Mary's Hospital, has successfully carried out over 700 BS sampling procedures in adults with a range of respiratory diseases. The technique has been very well tolerated, and has permitted cytokines and chemokines to be measured in the bronchial mucosal lining fluid (MLF).

Using a similar but smaller device we hope to take samples from infants ventilated due to severe RSV bronchiolitis. Babies ventilated with severe RSV infection, have an endotracheal tube (ETT) in position that requires suction clearance at regular intervals. Hunt Developments have developed a specialised device for introduction down the ETT, that can be used for BS in babies ventilated for severe RSV bronchiolitis.

As an initial step we will perform a pilot study on tolerability in ventilated infants, and have strict inclusion criteria which will allow inclusion of infants who are stable on the ventilator with low-moderate ventilation and oxygen requirements. We intend to compare inflammatory mediator levels in mucus that has been directly suctioned from the ETT, with levels of mediators in samples obtained using SAM by nasosorption and bronchosorption.

Genetics

Mendelian single gene deficiencies in the form of primary immunodeficiencies have demonstrated the important role that host genetics play in infectious disease outcome. More recently, single gene disorders predisposing to a narrow spectrum of infections have been described. Examples include defects in the IL12-IFN γ pathway predisposing to atypical mycobacterial infections, IRAK4-MYD88 defects to invasive pyogenic infections, and TLR3-IFN defects to herpes simplex encephalitis. Sequencing of the patient samples by whole exome/genome sequencing or linkage analysis will be carried out. One part of this study aims to identify genetic aetiologies of severe RSV infections which will provide tools for molecular diagnosis and genetic counselling.

Summary

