2. Epidemiology and virology: This study will assess the number of babies with upper respiratory tract infections (URTI) presenting to St Mary's Hospital ED, the number of babies with confirmed RSV hospitalised on the Paediatrics Ward and also the number admitted to the PICU. The study will assess the relative incidence of RSV A and B and allow us to determine whether RSV subtype is associated with disease severity.
3. Genetics: To establish whether there is a genetic predisposition to severe RSV infection. To carry out genetic analysis by targeted gene sequencing, next generation sequencing or whole genome SNP typing in order to evaluate any genetic deficiencies.
4. Correlation of qPCR with clinical severity

STUDY DESIGN

Type of Study: Pilot study

Duration: To take place in RSV infection season between October and March, starting in October 2015.

Identification of patients: We shall obtain our study groups from patients attending St. Mary's Hospital, London.

Number and types of Subjects:

A total of 5 participant groups (n = 30 in each group)

Details of each group and respiratory sampling procedures are given below:

- *Group 1:* Babies with suspected respiratory tract infection (RTI) in the ED:
 - Nasosorption (NS) in each nostril
 - NPA
- *Group 2:* Babies with diagnosed RSV infection admitted to paediatric wards:
 - NS (2 to 3 times daily, 4-6 hours apart)
 - NPA daily
- *Group 3:* Babies with diagnosed severe RSV infection in PICU requiring mechanical ventilation:
 - NS (2 to 3 times daily, 4-6 hours apart)
 - NPA daily
 - Bronchial aspirate (BA) daily
- *Control Group 1:* Babies without respiratory symptoms, attending routine outpatient appointments or undergoing elective surgical procedures:
 - Nasosorption (NS) only once
- *Control Group 2 :* Babies without RSV infection but requiring mechanical ventilation in PICU:
 - NS (2 to 3 times daily, 4-6 hours apart)
 - NPA daily

Bronchial aspirate (BA) daily

PROCEDURES

Sampling by Absorption:

Nasosorption: SAM strips will be placed inside each of the nostrils for up to 30 seconds. We will place the SAM on the inferior aspect of the inferior turbinate and middle turbinate. There is minimal discomfort in sampling in these areas. This is a well-tolerated, non-invasive procedure without the need for local anaesthetic.

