- NB – in the event of an exclusion to carrying out bronchial aspirate, (i.e: Significant hypoxia or instability precluding ventilator disconnection
- Transcutaneous oxygen saturation of <95% on 60% oxygen
- Risk of bleeding
- Pneumothorax);

As long as there is no contra-indication to carrying out NPA or nasal SAM sampling, then these children can still be included in the study, but will not require bronchial sampling.

Control Group 1

Inclusion criteria

- Babies, aged 2 weeks-24 months, attending routine outpatient appointments or undergoing elective surgical procedures.

Exclusion criteria

- Any respiratory symptoms
- All other exclusion are the same as Groups 1 and 2

Control Group 2

Inclusion criteria

- Infants aged 2 weeks-24 months.
- Infants ventilated on the PICU for any condition
- Confirmed RSV negative by PCR of respiratory tract samples

Exclusion Criteria

- All exclusions are the same as Group 3
- In addition – any concern about raised intracranial pressure

DATA STORAGE

Anonymised data will be stored in Redcap in the Department of Paediatrics at Imperial College London. The database will be password protected and will be web-based. Only those directly involved in the study will be able to access the data. Individuals will only be identified on the database by their unique alphanumeric identifier; data relating to the subjects' names to this identifier will be stored separately. Any data generated may be stored indefinitely and shared with other researchers outside of the participating sites. This will be done through databases such as ENA and EGA. Any data made available on these databases will be strictly confidential.

DATA ANALYSIS

Levels of inflammatory mediators (e.g. cytokines as pg/ml) across the patient groups will be presented as:

- Raw data: linear and log plots as appropriate
- Box-whisker plots: median/quartile/range
- Heat maps to show correlation between levels of mediators

Statistical analysis will be performed to demonstrate significance of levels of individual biomarkers and molecular signatures.

Data and all appropriate documentation will be stored for a minimum of 10 years after the completion of the study, including the follow-up period.

WITHDRAWAL CRITERIA

Any clinically significant side effects during procedures or withdrawal of consent by the parents or guardians of participants.

ADVERSE EVENTS

DEFINITIONS

Adverse Event (AE): any untoward medical occurrence in a patient or clinical study subject.

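### Group 3 eligibility does not require RSV illness to be the reason for ventilation, so incidental RSV can be counted as severe RSV in the secondary analyses

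*Combined protocol and SAP*

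**What the plan says.** All references are to the combined protocol and SAP.

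- **Background, on bronchosorption:** the intended population is "infants ventilated due to severe RSV bronchiolitis".
- **Study Design, Number and types of Subjects:** Group 3 is labelled "Babies with diagnosed severe RSV infection in PICU requiring mechanical ventilation", with 30 infants planned, as in each of the five groups.
- **Inclusion and Exclusion Criteria, Group 3:** infants admitted to the PICU, "aged 2 weeks-24 months with documented RSV infection (by rapid test and/or PCR"); "Infants of weight >2kg"; and "On a conventional ventilator with an Endotracheal Tube (ETT") of at least 2.0 mm. The exclusions cover sampling safety, prematurity, instability, recent oral steroids, consent and limited life expectancy. None concerns the cause of ventilation.
- **Inclusion and Exclusion Criteria, Control Group 2:** "Infants ventilated on the PICU for any condition", provided that PCR confirms the infant is RSV negative. Concern about raised intracranial pressure is an added exclusion for this group only.
- **Aims and Secondary Endpoints:** severity is to be correlated with quantitative PCR and related to RSV subtype. The genetic endpoint is "To establish whether there is a genetic predisposition to severe RSV infection".
- **Data Analysis:** mediator levels are to be presented across the patient groups. No severity score is defined, and there is no rule for reclassifying an infant after enrolment.

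**The concern.** The background and the group label both name a cause: RSV disease severe enough to need ventilation. The listed criteria name a coincidence: a ventilator and a positive test. During the RSV season an infant ventilated after surgery, for example, could carry the virus without RSV having caused the ventilation. For that infant the test result alone separates a ventilated control from a severe RSV case.

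Several secondary questions rely on Group 3 being what its label says. If the group is a mixture, its viral loads, subtype distribution, mediator profile and genotypes no longer describe severe RSV alone. The protocol allows data to be kept indefinitely and shared through public archives, so a wrong phenotype label could outlast the study.

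**Working it through.** **1. Text check.** Take an infant of 6 months and 7 kg, ventilated conventionally for a condition other than RSV, with a positive RSV PCR and none of the listed exclusions.

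| Requirement | Group 3 | Control Group 2 |
|---|---|---|
| Age 2 weeks to 24 months | met | met |
| Weight above 2 kg | met | met |
| Ventilated on PICU | met | met (any condition) |
| RSV status | positive required: met | negative required: **fails** |
| RSV is the cause of ventilation | not asked | not applicable |

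The only ventilated group open to this infant is Group 3. No Group 3 exclusion changes that.

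**2. How many.** There is no figure in the plan to reproduce: n = 30 is given without a power calculation, and no rate of incidental RSV is stated. Let m be the assumed share of incidental cases in Group 3. The expected number is 30m, and the chance of at least one, treating infants as independent, is 1 − (1 − m)^30.

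| m (assumed) | Expected of 30 | Left as severe RSV | Chance of at least one |
|---|---|---|---|
| 5% | 1.5 | 28.5 | 79% |
| 10% | 3 | 27 | 96% |
| 20% | 6 | 24 | 99.9% |

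For genetics, 30 is itself an upper limit, because research blood is tied to routine blood tests and genetic analysis is subject to consent.

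**3. Effect on a contrast of means.** Write S for the mean in truly severe infants, M for the milder comparison group and I for incidental cases. The observed difference is

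(1 − m)S + mI − M = (S − M) − m(S − I).

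- If I = M, this is (1 − m)(S − M), so the difference shrinks by the share m.
- If I lies above S, with S above M, the difference grows. The direction therefore depends on I, which the documents do not give.

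**4. Illustration for I = M.** With 30 against 30 and a two-sided 5% test, the standardised difference detectable with 80% power is (1.960 + 0.842) × √(2/30) = 0.723. Diluted power is Φ(2.802(1 − m) − 1.960).

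| m (assumed) | Diluted difference | Power |
|---|---|---|
| 0 | 0.723 | 80% |
| 5% | 0.687 | 76% |
| 10% | 0.651 | 71% |
| 20% | 0.579 | 61% |

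These figures show scale only. The plan specifies no such test, and it presents mediators as medians, quartiles and ranges.

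**The case against.** - **The label already limits entry.** Staff who follow the Study Design would not regard a postoperative infant with an incidental positive swab as having diagnosed severe RSV. The study is at one hospital and is coordinated by a consultant paediatrician and intensivist. This stands as far as it goes. A reader might infer that incidental cases do enter Group 3, but the documents show only that they can. Eligibility should still not depend on staff reading a label more strictly than the criteria.
- **Phenotyping is planned.** Under Blood Genetics Methods, clinical data are to be collected to characterise phenotypes. This is a partial safeguard for genetics, but no rule says how the data would decide who has severe RSV.
- **Severity is not equated with group membership.** This is correct. A clinical score could place an incidental case properly. But no score is defined, which leaves the group as the only working severity class.
- **The direction of bias is uncertain.** A reader might infer that every severity analysis is pulled towards no association. The documents do not support that. The background notes that viral load peaks before maximal symptoms in experimentally infected adults, so an incidental case sampled early could have a high load. Another critical illness could move mediators either way. Mild incidental cases in Group 2 would widen a contrast between Groups 2 and 3.
- **It is a pilot and the primary endpoint is safe.** SAM and NPA are compared in the same infant, so the reason for ventilation matters little there. This limits the importance of the point but does not remove it, because the secondary aims are stated aims.

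**Conclusion.** The point holds as a mismatch between the intended Group 3 population and the criteria that define it. Incidental RSV can be counted as severe RSV, and nothing later in the plan corrects this. The number is unknown. The range of 1.5 to 6 of 30 rests wholly on an assumed share of 5% to 20%. The loss of power from 80% to between 76% and 61% further assumes that incidental cases resemble milder RSV and that means are compared.

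The effect is confined to the secondary analyses that use Group 3 as the severe stratum. A reader might infer that the primary endpoint is compromised, but the within-infant comparison does not support that. Nor is Group 2 open to the same criticism in full: its label does not claim that RSV caused the admission, so its criteria do not contradict it. The point is worth acting on mainly because the remedy is nearly free.

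**What to change.** Reconcile the Group 3 inclusion criteria with the background and the Study Design label as follows.

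1. Keep RSV-positive ventilated infants eligible for sampling, so that none is lost to the comparison of SAM with NPA or left without a group.
2. Add one case-record field: whether RSV respiratory illness is the main reason for ventilation, in the treating clinician's judgement.
3. State in Data Analysis that the severity, subtype-severity, mediator and genetic analyses of Group 3 are limited to infants for whom the answer is yes, and report how many are set aside.

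A required interval between the RSV test and intubation is not needed. The documents give no basis for choosing one, and it could remove severe cases that were tested late. A parallel field for the reason for admission in Group 2 is optional.

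The cost is one field and one sentence. The downside is that a few infants may leave the severity and genetic sets, and that the field rests on clinical judgement.
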